A Prospective Observational Study of the Implementation of Telehealth-Supported LARC Provision in School-Based Health Centers

NCT04840836

IRB approval: Jan 5, 2024

1. Study Purpose and Rationale

Study Purpose

In this proposed prospective observational study, we will describe in detail the implementation of a **hybrid model of telehealth-supported long-acting reversible contraception (LARC) service provision in a network of 6 school-based health centers (SBHCs)** in New York City that serve adolescents and young adult high school students age 13-22 years (hereafter referred to as “adolescents”). We will use quantitative and qualitative data, leveraging surveys combined with electronic health record data, to assess satisfaction with telehealth-supported LARC care, and uptake and continuation of LARC methods following introduction of telehealth-supported LARC service delivery in SBHCs. The findings from this study, given the SBHC setting, have the potential to inform and improve LARC service delivery for adolescents far beyond New York City and the SBHC setting.

Specific Aims:

Aim 1. Quantify uptake of LARC (contraceptive implant, IUD) within the SBHC network following implementation of telehealth-supported LARC provision.

Aim 1.1 Among all patients who had a telehealth visit for contraceptive counseling, quantify the number and rate of telehealth LARC consultations and LARC initiations overall, and compare by LARC type (contraceptive implant vs. IUD).

Aim 1.2 Subgroup analyses of LARC initiation (overall and by type) by patient characteristics (e.g. age group, race/ethnicity, sexual activity in last 90 days).

Aim 2: Describe the implementation of telehealth-supported long-acting reversible contraception (LARC) service provision in school-based health centers (SBHCs) using mixed methods.

Aim 2.1 Assess, through quantitative surveys among LARC initiators, patients’ experience and satisfaction with telehealth-supported care.

Aim 2.2 Explore, through qualitative surveys with a purposive-sampled subset of LARC initiators, adolescents’ experience with the telehealth-supported care and perceived benefits and drawbacks of telehealth care overall and for supporting LARC services (Ambresin et al., 2013).

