The rapid initiation of telehealth services, precipitated by the COVID-19 emergency, represents a **novel opportunity** to assess a “hybrid” care model that eliminates the need for two in-person visits to the office setting, while also providing sufficient time to support patient education, decision-making, and screening prior to the LARC insertion visit, specifically among adolescents. This work can inform **youth-friendly reproductive health care** (Ambresin et al., 2013) more broadly, building on our prior work on providing youth-friendly contraceptive care in SBHCs (Sangraula et al., 2017). Providing youth-friendly reproductive health care to adolescents via telehealth is a field that is in its infancy (Barney et al., 2020; Williams, Meredith, Ott 2018), and the field has called for national organizations to develop guidance on **best practices in using telehealth** to deliver sensitive care to adolescents (World Health Organization, 2020).

School-based health centers (SBHCs) -- of which there are more than 2,580 in urban (46%), rural (36%) and suburban (18%) areas in the United States (Love, Schlitt, et al., 2019) reaching more than 6 million school-aged youth -- represent a unique opportunity to assess the promise of a hybrid model of reducing barriers to initiation of LARC among adolescents to **inform broader replication in other clinical settings**. SBHCs provide a wide range of reproductive health services, including pregnancy testing (80%) and contraceptive counseling (70%) (Love, Suleimanpour, et al., 2019).¹ And, almost half of SBHCs used some telehealth in 2017 (Love, Panchal, et al., 2019), so the networks are well-positioned to integrate telehealth-supported LARC services. This implementation model, therefore, has the potential for replication and scale-up with wide reach. Analyses of continuation by telehealth experience (Aim 4), coupled with the findings from the mixed methods surveys and interviews (Aim 2) will **inform modifications to the telehealth model** before replication.

2. Study Design and Statistical Procedures

This is a prospective observational cohort study that will include all enrolled SBHC patients at the 6 participating SBHCs who receive a telehealth reproductive health visit in the 12-month period following IRB-approved study initiation date, and will follow over a 6-18-month period all patients who initiate a LARC method during the study period.

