This two-year study will have three phases: 1) a 4-month study initiation phase; 2) a 12-month enrollment and surveying phase; 3) and a 6-month follow-up observation phase. Continuation analyses will rely on person-time, so that study participants will contribute a minimum of 6 to a maximum of 19 months observation time, depending on their time of enrollment.

Statistical Procedures. [name] will have lead responsibility for conducting statistical analyses, supervising data cleaning, and logic checks conducted by the Research Coordinator, and working with the Biostatistician on model building. As this is a prospective observational study that seeks to enroll all patients who receive telehealth-supported LARC services over a 12-month period, the sample size will be determined by patient flow and participation rates.

Aim 1 (Secondary Outcome): Quantify uptake of LARC (contraceptive implant, IUD) within the SBHC network following implementation of telehealth-supported LARC provision

Aim 1.1 Making use of a newly-implemented electronic health record (EHR) system, Epic, we will assess uptake of contraception, quantifying the number and proportion of contraceptive method initiation (uptake), assessing each month:

- 1) absolute number of contraceptive counseling visits via telehealth;
- 2) absolute number of LARC telehealth consultations (a LARC consultation being defined as a visit in which an insertion is scheduled);
- 3) absolute number of LARC initiations by type (contraceptive implant, IUD);
- 4) LARC initiation visits as a proportion of contraceptive counseling visits (overall, and by LARC type [contraceptive implant, IUD]);

¹ The current SBHA Census does not provide data on how many SBHCs dispense contraception; the most recent data on this are from the 2007-08 census and are not presented here.

- 5) LARC initiation visits as a proportion of all contraceptive method initiation visits (overall, and by LARC type);
- 6) LARC initiation visits as a proportion of LARC telehealth consultations (defined as a visit in which a LARC initiation was scheduled; overall and by LARC type);

and 7) relative share of initiations of contraceptive implant and IUD, among LARC initiators.

Statistical Methods (Aim 1.1)

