With a sample size of 102 and the margin of non-inferiority of 10 percentage points, the proposed study has 80% power to declare the non-inferiority of the telehealth-supported LARC services in a network of SBHCs in a one sample, one-sided Z test. This power analysis is for the primary efficacy outcome of interest, i.e., LARC continuation rate at 12 months. The reference LARC continuation rate at 12 months of 0.853 was obtained from the meta analysis conducted by Usinger, Gola, Weis & Smaldone in 2016. The studies included in their meta-analysis collected sample in the US with participants in those studies being young women aged 25 years and younger using a range of contraceptive methods. Therefore, if the true LARC continuation rate at 12 months is 0.753 or higher, the study is adequately powered to establish the non-inferiority of telehealth-supported approach. In the CHOICE Project, 12-month continuation of Copper IUDs among participants age 14-19 was 75.6% (Rosenstock et al., 2012).

Aim 3.2 (Exploratory, pending feasibility) Continuation compared to pre-Telehealth. Pending examination of the feasibility of constructing a pre-telehealth research database using the prior EHR system, compared to continuation rates within the same network prior to the implementation of telehealth-supported care, we will compare 12-month continuation (yes/no) following introduction of telehealth to 12-month continuation among LARC initiators seen the 18 month period prior to introduction of telehealth (June 2018-December 2019) *pending ability to export data from the prior electronic health record.*

3. Study Procedures

AIM 1

Participant enrollment – Aim 1: All patients who receive care at the SBHC provide informed consent for care, as well as record review for quality assurance purposes. Analyses for Aim 1 will include all female patients who have a “reproductive health visit,” which includes contraceptive counseling, contraceptive management, or contraceptive method initiation, during the study period. All patients who have a telehealth consultation with a SBHC medical provider for LARC services (conservatively estimated n=113) will be considered enrolled patients once the data are extracted from the EHR, and these will inform uptake analyses for Aim 1.

AIM 2

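### The Aim 1 uptake population is stated in four ways, and item 6 (possibly item 4) divides LARC initiations that need no telehealth visit by telehealth-only visits

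*Combined protocol and SAP*

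**What the plan says.** Aim 1, LARC uptake, is labelled a secondary outcome in section 2. The combined protocol and SAP describes its population in four ways:

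- **Section 1, Aim 1.1, under Specific Aims:** "Among all patients who had a telehealth visit for contraceptive counseling, quantify the number and rate of telehealth LARC consultations and LARC initiations overall".
- **Section 2, opening paragraph on design:** patients "who receive a telehealth reproductive health visit in the 12-month period following IRB-approved study initiation date".
- **Section 3, AIM 1, first statement on analysis:** "Analyses for Aim 1 will include all female patients who have a “reproductive health visit,” which includes contraceptive counseling, contraceptive management", and also method initiation. No telehealth condition is attached. Eligibility criterion 4 in section 4 has none either.
- **Section 3, AIM 1, next sentence:** "All patients who have a telehealth consultation with a SBHC medical provider for LARC services (conservatively estimated n=113) will be considered enrolled patients", and "these will inform uptake analyses for Aim 1".

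The uptake measures are listed in section 2 under Aim 1.1 and are assessed monthly. Item 1 counts counseling visits held by telehealth. Item 3 counts LARC initiations by type. Item 4 is "LARC initiation visits as a proportion of contraceptive counseling visits", without repeating the telehealth limit. Item 5 uses initiation visits for all contraceptive methods as its denominator. Item 6 is "LARC initiation visits as a proportion of LARC telehealth consultations", where a consultation is a visit at which an insertion is scheduled. Step 3 of the Aim 1.1 statistical methods then compares implant with IUD on items 4 to 7 by Chi-square tests.

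**The concern.** Aim 1 should report what share of patients seen by telehealth go on to start LARC. That share is a proportion only if everyone in the numerator is also in the denominator. The item definitions do not require this, and the broad population in section 3 permits the opposite. An insertion that followed in-person counseling would count as a LARC initiation visit, yet could never appear among the telehealth consultations.

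Two things are at stake. First, item 6 would overstate conversion from telehealth consultation to insertion, by an amount that depends on how many insertions bypass telehealth. Second, a Chi-square test by LARC type needs a cell for those who did not initiate. If that cell is obtained by subtracting an unlinked numerator from the denominator, it is too small, and it becomes negative if the numerator is the larger. Two analysts following different sections could also produce different tables from the same export.

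**Working it through.** **Inputs from the documents.** Planned telehealth LARC consultations: 113 (sections 3 and 4). Planned LARC insertions: 102 (section 4). The plan states no value for item 6 and no derivation of either count, so there is no published percentage to reproduce.

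**Step 1: item 6 on the planned counts.** 102/113 = 0.903, or 90.3%. This is a conversion proportion only if all 102 insertions come from the 113 consultations.

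**Step 2: effect of unlinked insertions.** Let x be the number of LARC insertions, beyond the planned 102, in patients with no telehealth LARC consultation. The documents do not give x; the values below are assumptions. All 102 planned insertions are taken to follow a consultation. Under the broad population:

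item 6 = (102 + x)/113

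- x = 0: 102/113 = 90.3%
- x = 5: 107/113 = 94.7%
- x = 11: 113/113 = 100.0%
- x = 12: 114/113 = 100.9%
- x = 20: 122/113 = 108.0%

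The ratio passes 100% at x = 12, when 12 of 114 initiations (10.5%) have no telehealth consultation. With the numerator restricted to patients in the denominator, it stays at 90.3% whatever x is.

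**Step 3: item by item.**

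- *Item 6.* The denominator is explicitly telehealth and the numerator is not. Of the four populations, only the group of 113 makes the ratio nested by construction.
- *Item 4.* If the denominator is the telehealth visits of item 1, the mismatch is the same as in item 6. If it is all counseling visits, the ratio no longer measures telehealth uptake.
- *Item 5.* Numerator and denominator are both initiation visits, so it cannot exceed 100%. Its meaning still depends on the population chosen.
- *Item 7.* This is the split of LARC initiators by type, so it is nested.

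**Step 4: monthly reporting.** Even with a single population, an insertion can fall in a later month than its consultation. A month with few consultations and several insertions carried over can show more than 100%. Fixing the population does not remove this; each initiation has to be tied to its telehealth visit.

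**The case against.** The best defence is that the plan is about telehealth throughout. Section 1, the design paragraph and the second sentence in section 3 all set a telehealth limit, and the broad sentence may only describe the record extract, which item 5 needs. Item 4 reads naturally as referring back to item 1. This is a fair account of what was probably meant. It does not settle what is written: the broad sentence is expressly about who is in the Aim 1 analyses, eligibility criterion 4 repeats the omission, and nothing links item 6 initiations to their consultations.

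A reader might infer more than the documents support:

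- *That the Aim 1.2 subgroup tests are biased.* The introductory wording of Aim 1.2 is loose, but its methods paragraph tests initiators out of those who had the relevant consultation, which is nested.
- *That patients seen only for contraceptive management, including current LARC users, dilute uptake.* They enter no denominator in items 4 to 7.
- *That item 6 is expected to exceed 100%.* The planned counts give 90.3%. The 129 initiations of 2018-19 predate telehealth and say nothing about how many insertions would bypass it.

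**Conclusion.** The concern holds as an inconsistency in the current text with a possible, unquantified bias in a secondary outcome. The Aim 1 population has four descriptions that cannot all apply. Item 6, and item 4 if its denominator is telehealth visits, are not nested under the broad one, and this carries into the implant versus IUD Chi-square tests. The size rests entirely on the assumed number of insertions without a telehealth consultation. If sites route every insertion through telehealth, the bias in item 6 over the whole period disappears and only the conflicting text and the monthly timing problem remain. The primary 12-month continuation test is not challenged by this point.

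**What to change.** - Reconcile section 1 (Aim 1.1), section 2 (design paragraph and Aim 1.1 items), section 3 (AIM 1) and section 4 (eligibility criterion 4) to one telehealth-based Aim 1 population.
- For items 4 and 6, count an initiation only if that patient had the corresponding telehealth visit beforehand: a counseling visit for item 4, a visit at which insertion was scheduled for item 6. Count patients rather than visits, and say so, since the items now count visits.
- Index monthly figures by the date of the telehealth visit, not of the insertion.
- Keep the broad reproductive health visit extract as the data source and for the item 5 denominator.
- Report LARC initiations with no earlier telehealth visit as a separate count.

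The cost is a wording change and some additional linkage by visit type and date, which the export of all visits planned in section 3 (AIM 3) should allow. Reported uptake may be slightly lower. No new exclusion is needed, and recruitment and sample size do not change.

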Aim 3: Quantify LARC continuation over a 6-18 month follow-up period among LARC initiators within the SBHC network following implementation of telehealth-supported LARC provision. Using EHR data for all patients who initiated LARC, we will use Kaplan-Meier survival curves to assess LARC discontinuation overall, and Cox proportional hazard models to compare LARC continuation by LARC type.

Aim 3.1 (Primary Efficacy Outcome): 12-month continuation of LARC using telehealth-supported care among SBHC patients compared to LARC continuation rates among adolescents age 25 years and under as documented in a recent meta-analysis. Continuation rates will be expressed both as rates at 6 months and 12 months post-initiation, and using Kaplan-Meier curves to model discontinuation. Continuation rates in this setting will be compared to rates from a recent meta-analysis among adolescents and young adults that found 12-month continuation rates of 85.3% (primary efficacy outcome) for contraceptive implants and IUDs in the US-based studies (Usinger, Gola, Weis & Smaldone, 2016).

Aim 3.2 (Exploratory, pending feasibility) Continuation compared to pre-Telehealth. Compare 12-month continuation rate following introduction of telehealth to 12-month continuation among LARC initiators seen during the 18 month period prior to introduction of telehealth (June 2018-December 2019) *pending ability to export data from the prior electronic health record.*

Hypothesis:

We hypothesize that, in this sample of adolescents receiving telehealth-supported LARC services in a network of SBHCs, the LARC continuation rate at 12 months will be non-inferior to the 12-month continuation rate among adolescents and young adults age <25 (85.3%) as documented in a meta-analysis

comparing contraceptive implants and IUDs, in the absence of telehealth. The non-inferiority margin is chosen to be 10 percentage points less than that of the current standard of care (SOC) in US as such difference represents the maximum tolerable margin for inferiority while clinically important impact of proposed intervention can still be preserved.

Background/ Rationale

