Thematic analysis will be used to describe the qualitative data generated from the interviews. Using an inductive approach, two coders will scan a random selection of transcripts to generate initial codes; working from these, we will generate a code-book that lists major themes, specifies categories

emerging from the data, and descriptions of each theme. The first 10 transcribed interviews will be jointly coded using Dedoose; then, inter-rater coding agreement will be assessed. The entire study team will: resolve discrepancies in coding, clarify theme definitions, and collapse or expand themes as needed.

Primary efficacy outcome (Aim 3): Continuation post-LARC initiation

The primary outcome for this study (3.1) will be absolute continuation rate 12 months post-initiation (dichotomous yes/no continuation), with analyses also examining continuation at 6 months (yes/no).

Aim 3.1 (Primary Efficacy Outcome): Overall 12-month continuation of LARC using telehealth-supported care compared to LARC continuation rates among adolescents age 25 and under as documented in a meta-analysis of US studies.

The primary outcome will be the proportion of patients continuing their initiated LARC method at 12 months post-initiation. Hypothesis: We hypothesize that, with the non-inferiority margin of 10 percentage point difference, in this sample of adolescents receiving telehealth-supported LARC services in a network of SBHCs, the LARC continuation rate at 12 months will be non-inferior to the reported 12-month continuation rate among adolescents and young adults age under 25 years (85.3%) in the US who initiated contraceptive implants or IUDs the absence of telehealth (Usinger, Gola, Weist & Smaldone, 2016).

Statistical Methods (Aim 3.1):

Continuation rates will be expressed as rates at both 6 months and 12 months post initiation, and time to discontinuation will be visualized using Kaplan-Meier curves.

We will test the primary null hypothesis $H_0: p \leq 0.753$ (i.e., 10 percentage points less than the reference rate of 0.853) using one-sample, one-tailed Z-test, where p is the LARC continuation rate at 12 months for participants who receive telehealth-supported LARC services in a network of SBHCs, and the reference the proportion (of 0.853) was chosen from the finding of the meta-analysis mentioned above.

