Follow-up observation (Continuation Analyses, Aim 3): Follow-up observation will continue for 6 months after the enrollment phase has completed; therefore, participants enrolled in the first month will have 18 total months observation, while those enrolled in the last month will have 6 months. In 2018-19, in the network of 6 SBHCs, 2,425 unique female patients had a total of 12,398 visits (for any purpose), representing an average of 5 SBHC visits per female patient in the academic year.² At each visit to the SBHC, regardless of visit type, all female patients have their medications, including contraceptive method, reconciled and confirmed in the medical record. With the new Epic EHR system, export of all LARC-related procedure codes (insertions, removals, removal with replacement) and device codes (e.g. Nexplanon, Liletta, Paragard) *in addition to all visits* (with corresponding data on current contraceptive method) will enable us to identify person-time events including censoring. At all New York Presbyterian (NYP) sites, the health care provider is required to conduct reconciliation of medications and document it in the EHR at every visit. The SBHC medical providers ask every SBHC patient at every visit what their current contraceptive method is – confirming the presence of the method, and documenting this in two places in the EHR (in the contraception history section, and in the medications section).

Compensation.

All Aim 2 survey and interview participants will receive compensation for their time and effort in the form of an Amazon electronic gift card, purchased through the Mailman School of Public Health. Compensation is as follows:

Quantitative survey participants will receive, as compensation for their time and effort, an Amazon gift card valued at \$10 at the conclusion of the survey. The card will be sent to participants electronically.

Qualitative interview participants will receive, as compensation for their time and effort, an Amazon gift card valued at \$25. The card will be sent to participants electronically.

4. Study Subjects

Subject Population Justification:

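### The primary 12-month yes/no test assumes full data on 102 patients, but about half cannot be observed to month 12, and the planned censored-data methods are not tied to that test

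*Combined protocol and SAP*

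**What the plan says.** All references are to the combined protocol and SAP.

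- **Endpoint and test (Section 2, Aim 3.1 and its Statistical Methods).** "The primary outcome will be the proportion of patients continuing their initiated LARC method at 12 months post-initiation". It is described as dichotomous. The null value is 0.753, tested "using one-sample, one-tailed Z-test, where p is the LARC continuation rate at 12 months". In this section Kaplan-Meier serves to display time to discontinuation.
- **Power (Section 2, Power/Sample Size, Aim 3.1).** At n=102 and a 10-point margin, 80% power is claimed, with full data expected for all 102. The support given is that medications and contraceptive method are reconciled at each visit. The same section lists device removal as an example of censoring.
- **Calendar (Section 2 opening; Section 3, AIM 3).** There is a 12-month enrolment and then 6 months of observation. The study "will follow over a 6-18-month period all patients who initiate a LARC method during the study period", and "participants enrolled in the first month will have 18 total months observation, while those enrolled in the last month will have 6 months". One sentence in Section 2 gives the maximum as 19 months instead of 18.
- **Methods for unequal follow-up.** Section 1, Aim 3, says "we will use Kaplan-Meier survival curves to assess LARC discontinuation overall, and Cox proportional hazard models to compare LARC continuation by LARC type", and Aim 3.1 there mentions "using Kaplan-Meier curves to model discontinuation". Section 2 adds: "Continuation analyses will rely on person-time". Section 3, AIM 3, says censoring will be identified from the record.
- **Sample size.** Section 2 also says that "the sample size will be determined by patient flow and participation rates".

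**The concern.** A yes/no status at month 12 does not exist for a patient who is still using her method when observation ends at month 8. On the plan's own calendar this applies to most patients who start LARC in the second half of enrolment. Reconciliation at visits cannot supply a status after observation has stopped.

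The plan has the right tools, but no sentence says that the tested p is the Kaplan-Meier estimate, gives its variance, or allows for censoring in the power. The 12-month Chi-square and logistic comparisons of implant and IUD have the same gap. Listing device removal, which is the event, under censoring makes it harder still to infer the intended rule.

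This is the only primary hypothesis. How some 45 patients are handled decides both the bias and the power of the test, and without a written rule the choice could be made after the data are seen.

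**Working it through.** **Inputs from the plan:** p0 = 0.753, reference rate 0.853, n = 102, one-sided test, enrolment over 12 months, observation to month 18 from the start of enrolment.

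**Assumptions (not in the plan):** true rate p1 = 0.853, one-sided alpha 0.05, uniform accrual, constant hazard, no loss other than cut-off.

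**1. Reproduce the stated power.**

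Power = Φ{[(p1 − p0)√n − 1.645·√(p0(1−p0))] / √(p1(1−p1))}

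Here √(0.753×0.247) = 0.4313 and √(0.853×0.147) = 0.3541. At n = 102: (1.0100 − 0.7094)/0.3541 = 0.849, and Φ = 80.2%. The plan's 80% reproduces. At one-sided 0.025 the same formula gives 67.9%, so 0.05 is the likely intended level.

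**2. Who can be observed to month 12.** A patient enrolled at month e is observed for 18 − e months, which is at least 12 only if e ≤ 6. That is half: 51 of 102. With the 19-month maximum it is 7/13 of 102, or about 55.

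**3. Status of the other 51 at cut-off.** The monthly hazard is −ln(0.853)/12 = 0.01325. Mean continuation over follow-up of 6 to 12 months is (e^(−0.0795) − 0.853)/0.0795 = 0.888. So 51 × 0.112 = 5.7 have a recorded removal, and 51 × 0.888 = 45.3 are still using, with month-12 status unknown.

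**4. Patients with full follow-up only.** At n = 51: (0.7141 − 0.7094)/0.3541 = 0.013, and Φ = 50.5%. At n = 55 it is 53.6%.

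**5. Kaplan-Meier at 12 months on all 102.** This was simulated with follow-up uniform on 6 to 18 months (40,000 to 100,000 runs). The null-variance Z uses 0.753 × 0.247/n_eff, where n_eff = S(1−S)/Greenwood variance.

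| Test | Power | Size at a true 0.753 |
|---|---|---|
| Null-variance Z | about 73% | about 5% |
| Log-log lower limit | about 71% | about 4.5% |
| Plain Greenwood limit | about 79% | about 7% |

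Mean n_eff is 85.6. Putting 85.6 into the formula in step 1 gives 72.9%, which agrees. The plain Greenwood limit comes close to 80% only by exceeding its nominal size.

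**6. Sensitivity of the Kaplan-Meier power.**

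| Change from step 5 | Log-log | Null-variance Z |
|---|---|---|
| Weibull shape 0.5 | 74% | 76% |
| Weibull shape 1.3 | 69% | 71% |
| 65% of initiations in the first 6 months | 75% | 77% |
| 35% of initiations in the first 6 months | 66% | 68% |
| Other loss of 10% by month 12 | 68% | 71% |
| Other loss of 20% by month 12 | 65% | 68% |
| 129 initiators (the 2018-19 count) | 80% | 82% |
| 75 initiators (44 in seven months, annualised) | 58% | 61% |

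Under the 6-18 month calendar, 80% power needs about 129 initiators (log-log) or 123 (null-variance Z).

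**7. What an unwritten rule could do.** The plan states neither of these rules, but it excludes neither.

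- Keep late removals but drop late users: 51 × 0.853/(51 + 5.7) = 0.767, so a true 0.853 looks like 0.767.
- Count users at cut-off as continuing, with a true rate of 0.753: late patients average 0.809, and (0.753 + 0.809)/2 = 0.781. False non-inferiority is then about 15% (normal approximation) to 18% (simulation), against a nominal 5%.

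**The case against.** The best defence is that the plan already expects unequal follow-up. It says continuation analyses rest on person-time, puts Kaplan-Meier inside Aim 3.1, plans to identify censoring, and does not specify the variance of the Z-test. A Z-test built on a Kaplan-Meier estimate is therefore compatible with the text, and the full-data statement could mean complete capture of visits. On that reading the text is ambiguous, not wrong, and the 50% figure belongs to a rule the plan never states.

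Part of this stands. A full-follow-up-only analysis is one possible reading, not the plan's declared method, and 50% should be read as the lower of two cases. But the operative section calls the outcome dichotomous and uses Kaplan-Meier for display. Even the charitable reading gives about 71-73%, because the power calculation has no allowance for censoring.

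Other fair points:

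- Alpha, accrual pattern and hazard shape are not in the plan, so 71-73% is one scenario. At n=102 and one-sided 0.05, the variations in the sensitivity table run from 65% to 77%.
- The 80.2% is a normal approximation. The exact power of the planned test at n=102 is 83.7%, with exact size 5.8%. This does not rescue the claim, since it too needs all 102 outcomes.
- The 75-initiator case annualises months that the plan itself calls disrupted.
- Kaplan-Meier alone leaves a choice open. Status is confirmed only at visits, and footnote 2 in Section 4 expects fewer visits among LARC users, so the censoring date needs a rule as well.

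**Conclusion.** The concern holds and should be fixed before the primary analysis. The calendar, the dichotomous 12-month test and the expectation of full data on 102 patients cannot all be true, and this follows from the plan's own text without any assumption about rates.

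The size of the problem rests on the assumptions listed in the working. Under them, the claimed 80% becomes about 71-73% with a Kaplan-Meier estimate on all initiators, or about 50% with fully followed patients only. None of the variations tried at n=102 under the stated 6-18 (or 19) month calendar reaches 80% with the type I error held. With about 123 to 129 initiators it would.

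**What to change.** **Preferred change (wording only, using methods already named):**

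1. Make the Kaplan-Meier 12-month continuation probability in all LARC initiators the primary estimate.
2. Declare non-inferiority if a one-sided lower limit of stated type, or a null-variance Z, excludes 0.753 at a stated alpha. Avoid the plain Greenwood limit.
3. Define discontinuation as the event, and end of observation while still using as censoring. Correct the sentence that lists removal under censoring, and say how removal with re-insertion is classified.
4. State the censoring date for a user with no recent visit: last confirmed visit or data cut-off.
5. Replace the 80% with about 71-73% at n=102, list the assumptions, and note that it varies with the number of initiators. Remove the full-data statement, or limit it to capture of visits.
6. For implant versus IUD at 12 months, use the Cox model already planned, or a difference in 12-month Kaplan-Meier estimates if the 12-month risk is the target. The 6-month comparisons can stay.
7. Reconcile the 18- and 19-month maxima.

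The three phases add up to 4 + 12 + 6 = 22 months of a two-year study. If the remaining 2 months are free for observation, which the plan does not say, follow-up of 8 to 20 months raises power to about 75-77%.

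**Alternative:** keep the Z-test and continue the passive record extraction until the last initiator reaches 12 months. This takes up to 6 more months: 4 + 12 + 12 = 28 in total, 4 past the stated two years. It restores 80% only if month-12 status is recorded for all 102. By the formula above, power is 76% with 92 recorded and 71% with 82 (exact: 83.7%, 72.7% and 68.4% for 102, 92 and 82).
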